Phendimetrazine (PHEN), a Schedule III medication under the Controlled Substance Act, is indicated for treating obesity. After oral administration, PHEN is converted to phenmetrazine, which is largely responsible for its behavioral and neuropharmacological effects. Consistent with the notion that compounds with intermediate 5-HT/DA release ratios selectively attenuate the reinforcing effects of COC, phenmetrazine (5-HT/DA ratio = 37) completely eliminated COC-maintained responding in monkeys. Recent research with PHEN has also shown that the parent compound reduces COC self-administration. Moreover, PHEN does not maintain self-administration and produces only limited positive subjective effects compared to d-amphetamine in COC users, which suggests that its abuse potential is low. Although PHEN has yet to be tested as a potential pharmacotherapy for COC dependence in human laboratory experiments or clinical trials to our knowledge, the results of extant preclinical experiments suggest it is a viable option.

In an ongoing study, we have demonstrated that COC can be safely administered to patients maintained on 70, 140 and 210 mg PHEN/day. Whether PHEN attenuates the reinforcing effects of COC, the best predictor for treatment efficacy (Comer et al., 2008; Haney and Spearman, 2008), remains to be determined. **The specific aim of this study is to demonstrate that PHEN maintenance reduces the reinforcing effects of intranasal COC.** To accomplish this aim, we will conduct an experiment in which non-treatment seeking COC-using participants (N=36) will be maintained on doses of PHEN (0 and 210 mg/day [target dose, dose will be titrated up as described below]). The reinforcing and other behavioral effects of intranasal COC (0 [placebo], 20, 40 and 80 mg) will be determined after 7 days of maintenance on the target PHEN dose (i.e., 210 mg/day). In order to monitor the safety of the drug combinations, cardiovascular measures will be taken routinely throughout experimental sessions and subjects will complete a daily side effect scale with nursing staff. We hypothesize that PHEN will attenuate the reinforcing effects of COC, as well as other abuse-related effects of COC (i.e., positive subjective effects). We also hypothesize that COC will be well tolerated during active PHEN maintenance.

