## 7. RESEARCH PROCEDURES

*General Procedures.* Subjects that meet the inclusion criteria will participate as inpatients at the University of Kentucky CCTS Research Inpatient Unit (CRIU). Subjects will be discharged upon completion of the entire protocol.

This experiment will require each subject to participate for approximately five weeks. Experimental sessions will be conducted as outlined in Table 1 below. We would like to note that COC doses will both be given in random order, whereas order of PHEN dosing will be counterbalanced across subjects. We would also like to note that subjects may be maintained on a given PHEN condition for more than 11 days prior to session to avoid testing COC doses on weekends.

Day	Table 1. Experimental Procedures
1	Admission to the CRIU.
2	Practice Session.
3-17	Placebo maintenance. Placebo administered twice daily (0700 and 1900 hours).
14-17	Experimental Sessions. Reinforcing effects of intranasal COC (0 [placebo], 20, 40 and 80 mg) determined using progressive-ratio procedure.
18-32	PHEN maintenance. Administered in divided doses (0700 and 1900 hours). Subjects receive 35 mg twice daily for two days, then 70 mg twice daily for two days, then 105 mg twice daily for remainder of maintenance period.
29-32	Experimental Sessions. Reinforcing effects of intranasal COC (0 [placebo], 20, 40 and 80 mg) determined using progressive-ratio procedure.
33	Discharge

During their participation in the research protocol, subjects will not be allowed to leave the CRIU, nor will visitors be allowed, with the exception that subjects can leave for walks under clinical supervision and if approved by physicians. Research subjects will be allowed to make local telephone calls. After completing the research protocol, interested subjects will be offered a referral to an appropriate drug abuse treatment program.

All subjects will provide urine and expired air samples before and periodically during study participation. The presence of non-nicotine drugs of abuse or alcohol not administered experimentally in the research protocol will result in immediate termination from the research study.

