Subjects will be excluded from further research participation if at any time during the experimental sessions COC increases heart rate above 130 bpm, systolic pressure above 180 mmHg, diastolic pressure above 120 mmHg or if clinically significant and/or prolonged ECG abnormalities are noted. Subjects will remain seated for the duration of the experimental session. Between the sampling and self-administration phases, subjects will be allowed to eat a standard hospital lunch but will not be allowed to smoke. No experimental activities will be scheduled for the remainder of the day after a self-administration session, but subjects will receive their appropriate maintenance medication at 1900 hours. Subjects will be free to engage in recreational activities (e.g., watch television, read, listen to music, arts and crafts, play video or board games). Research subjects will be required to be in bed with the lights out by 2300 hours.

Time	Table 2-Daily Activities for Maintenance Days
0700	Patient awakened. Vital signs recorded. Medication administered if vitals are within range and no indication of sedation or withdrawal. Subject eats breakfast.
1200	Lunch is served.
1300	UKU completed.
1900	Dinner is served. Vital signs recorded. Medication administered if vitals are within range and no indication of sedation or withdrawal.
2300	Lights out.

Time	Table 3-Daily Activities for Experimental Days
0700	Patient awakened. Vital signs recorded. Medication administered if vitals are within range and no indication of sedation or withdrawal. Subject eats breakfast.
0900	Vital signs recorded. Computerized tasks completed. ECG monitoring begins.
0930	Vital signs recorded. 0 [placebo], 20, 40 or 80 mg intranasal COC administered if vitals are within range. Measures completed 0, 15, 30, 45 and 60 minutes after drug administration.
1030	Sampling phase ends.
1200	Lunch is served.
1300	UKU is completed.
1330	Vital signs recorded. Computerized tasks completed (including progressive-ratio task). ECG

	monitoring begins.
1430	Vital signs recorded. Portion of intranasal dose earned is administered if vitals are within range. Measures completed 0, 15, 30, 45 and 60 minutes after drug administration
1530	Session ends. Remainder of daily activities identical to those listed in Table 2.

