Progressive-ratio data (i.e., break point, number of COC doses earned) will be analyzed with two-factor mixed-model ANOVA with COC (within-subject variable; 0 [placebo], 20, 40 and 80 mg), and PHEN (within-subject variable; 0 and 210 mg/day) as the factors. A significant attenuation (i.e., rightward shift in the dose response) of the effects of COC will be inferred if the main effect of PHEN or the interaction of COC and PHEN attains statistical significance in the ANOVA. If the COC-PHEN interaction attains statistical significance, the mean square error term will be used to conduct Tukey's HSD *post-hoc* test to make appropriate pair-wise comparisons between means. Peak-effect and AUC data for the cardiovascular, performance and subjective effects measures obtained during the sampling phase will be analyzed in a similar fashion. Cardiovascular, performance and subjective effects data from the self-administration phase will not be analyzed because participants will likely ingest varying amounts of COC making these data difficult to interpret.

The primary outcome measures for this study are the break point and number of COC doses earned on the progressive-ratio procedure in subjects maintained on active PHEN or placebo. Considering the complete within-subject design, number of dose levels of each drug (i.e., two PHEN conditions and four doses of intranasal COC) enrolling 36 subjects will provide adequate power to detect an effect size ( $d$ ) of at least 0.44 for attenuation of the reinforcing effects of COC as a function of maintenance on PHEN and placebo ( $\text{power} = 0.80$ ,  $\alpha = 0.05$ , G\*Power). We used the results of a previous study conducted in our laboratory to determine an appropriate sample size for the present experiment ([name] et al., 2010). That study demonstrated that d-amphetamine maintenance decreased the reinforcing effects of COC with an estimated effect size ( $d$ ) of approximately 0.46.

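### Cardiovascular data after the self-administered COC dose are barred from analysis, so the tolerability hypothesis has no planned evidence at the highest same-day exposure

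*Combined protocol and SAP*

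**What the plan says.** Section 1 (Background) sets out a tolerability hypothesis: "We also hypothesize that COC will be well tolerated during active PHEN maintenance". It names two sources of safety information: "cardiovascular measures will be taken routinely throughout experimental sessions and subjects will complete a daily side effect scale with nursing staff". It gives the hypothesis no endpoint and no criterion.

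Section 7, Table 3, puts two COC administrations on each experimental day:

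- 0930: "20, 40 or 80 mg intranasal COC administered if vitals are within range", with 0 mg as the fourth level.
- 1300: "UKU is completed".
- 1430: "Portion of intranasal dose earned is administered if vitals are within range".

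Measures follow each administration at 0, 15, 30, 45 and 60 minutes.

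The Data Analysis part of Section 7 then treats the two phases differently. For the first: "Peak-effect and AUC data for the cardiovascular, performance and subjective effects measures obtained during the sampling phase will be analyzed in a similar fashion". For the second: "Cardiovascular, performance and subjective effects data from the self-administration phase will not be analyzed because participants will likely ingest varying amounts of COC". It describes no analysis of the UKU, adverse events, withheld doses or cardiovascular exclusions.

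**The concern.** The afternoon administration comes on top of the morning one, so the largest COC exposure of each day occurs in the phase that is barred from analysis. Section 9 says that side effects are dose-related and that they may be more frequent and larger when COC is combined with PHEN. The afternoon is therefore where evidence on tolerability would be most informative.

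The stated reason is that intake varies. That is a reason not to test PHEN against placebo in this phase, because the amount taken is chosen by the subject and is itself the primary outcome. It does not explain why readings already recorded should go unreported.

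At stake is the scope of a secondary conclusion. A report that COC was well tolerated on PHEN, supported only by the planned analysis, would describe a single sampled dose. It could be read as covering repeated same-day COC. The primary analysis is not affected.

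**Working it through.** All inputs come from Section 7: Table 1 (schedule), Table 3 (clock times) and the Self-Administration Phase paragraph (ten opportunities, each for one tenth of the sampled dose).

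**1. Reproduce the plan's own interval.** The Self-Administration Phase paragraph says that the phase starts four hours after sampling. Table 3 gives 0930 to 1330 = 240 min = 4 h. The two agree, so the Table 3 times can be used.

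**2. Timing around the afternoon dose.**

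- Sampled dose to UKU: 0930 to 1300 = 210 min.
- UKU to afternoon dose: 1300 to 1430 = 90 min.
- Sampled dose to afternoon dose: 0930 to 1430 = 300 min.
- Afternoon dose to the next day's UKU: 24 h − 1.5 h = 22.5 h.

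The same-day UKU therefore cannot reflect the afternoon dose.

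**3. Maximum same-day COC.** Sampled dose + 10 × (sampled dose / 10). On the 80 mg day this is 80 + 10 × 8 = 160 mg. The planned cardiovascular analysis covers the 80 mg sampled dose only.

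**4. Exposure per PHEN condition.** Sampled doses sum to 0 + 20 + 40 + 80 = 140 mg. Earned doses add at most another 140 mg. Up to 140 / 280 = half of the COC taken falls outside the analysis.

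**5. Occasions.** There are 8 sessions × 2 administrations = 16 occasions. Two of the 8 sessions use 0 mg COC, which leaves 6 × 2 = 12 active occasions. Of these, at most 6 are afternoon doses; the number is lower if a subject chooses money throughout a session or a dose is withheld.

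**6. Post-dose readings.** Table 3 schedules 5 time points after each dose, so 5 of 10 per session are analysed.

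**7. What else covers the afternoon dose, and whether the plan analyses it.**

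| Information | Covers the 1430 dose? | Analysis planned? |
|---|---|---|
| Vital signs, 0 to 60 min (Table 3) | Yes | No, expressly ruled out |
| ECG monitoring from 1330 (Table 3) | Yes | None described |
| Dose given only if vital signs are in range (Table 3) | Yes | No count of withheld doses |
| Exclusion for heart rate above 130 bpm, systolic above 180 mmHg, diastolic above 120 mmHg or ECG abnormality (General Procedures) | Yes, at any point in a session | No count of exclusions |
| Adverse events (Section 17, Safety Monitoring Plan) | Yes, throughout participation | None described |
| UKU at 1300 (Table 3) | Not on the same day | None described |

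**The case against.** The strongest reply is that the exclusion is disclosed and reasoned. PHEN is hypothesized to reduce COC taking, so an afternoon comparison would set different amounts of COC against each other and could make PHEN look better tolerated only because less was taken. This stands, and it is why any afternoon summary must be descriptive and shown with the mg taken.

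A reader might go further and infer that the afternoon dose is unmonitored, or that the plan decides tolerability from the morning dose alone. The documents support neither reading. Vital signs, ECG, the in-range condition, the exclusion rule and adverse event collection all cover the afternoon, and nothing says that the sampling-phase ANOVA decides the hypothesis. The gap is in planned analysis, not in monitoring.

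The size is also easy to overstate. Counting 8 of 16 administrations includes placebo-COC sessions. The figure of 160 mg is a ceiling: it needs all ten choices for drug, or 10 × (400 + 1300) / 2 = 8,500 responses, and in-range vital signs. The two doses are five hours apart, and the documents do not show that their effects add.

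A reader might also infer that the UKU systematically scores afternoon effects under the wrong condition. In the Table 1 schedule, the day 17 afternoon is next rated on day 18, under the other maintenance condition. A COC-on-PHEN effect could be rated under placebo maintenance there only in subjects who receive PHEN first. For the last session, Section 7 calls the UKU daily and Table 1 lists discharge on day 33; whether a UKU is done that day is unstated, not excluded.

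Moving the UKU to after the session is tempting but not a clear gain. No recall window is given and no UKU analysis is planned. A later rating would also mix the randomised sampled dose with a self-chosen amount that is expected to fall under PHEN.

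**Conclusion.** The point holds for the planned analysis. Section 1 states a tolerability hypothesis, and the Data Analysis text rules out any use of cardiovascular readings after the 1430 dose, when same-day COC is highest. Up to 6 of 12 active-COC occasions per subject and 5 of 10 scheduled post-dose time points per session are affected, with a same-day maximum of 160 mg against the 80 mg covered. These figures assume that all eight sessions are completed; the COC amounts also assume that every choice is for drug and that no dose is withheld. Actual intake cannot be known in advance.

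The importance is moderate. Tolerability appears as a hypothesis in Section 1; it is not the primary objective in Section 2 or a primary outcome in Section 7. The documents do not support a claim that subjects are unprotected in the afternoon or that the primary result is at risk.

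**What to change.** In the Data Analysis part of Section 7:

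1. Limit the exclusion of self-administration data to the inferential PHEN-by-COC ANOVA.
2. Add a descriptive safety summary of the self-administration phase, by PHEN condition and sampled COC dose, shown with the mg of COC actually taken. It should give:
   - peak heart rate and blood pressure;
   - the number of readings above the exclusion limits already in General Procedures;
   - afternoon doses withheld because vital signs were out of range;
   - exclusions under the cardiovascular rule;
   - adverse events with onset after the afternoon dose.
3. Include subjects who do not complete. Section 4 sets its target in completers, and exclusions would otherwise drop out of the table.
4. Base the tolerability statement on both phases, or restrict it explicitly to the single sampled dose.
5. Leave the UKU at 1300, and state as a limitation that it does not capture same-day effects of the afternoon dose.

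The cost is one descriptive table from information that the protocol already provides for collecting. The documents do not say whether adverse event forms record a clock time, and assigning events to the afternoon depends on that. The downside is that the afternoon comparison remains descriptive, because intake is chosen by the subject and may differ by PHEN condition. No dose, clinical limit or procedure changes.

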**Vital Signs.** Heart rate, blood pressure, oral temperature and heart rhythmicity (via ECG) will be recorded using a Dinamap digital monitor (Critikon, Pro 1000, Tampa, FL). These measures will be completed at as described in the tables above. Telemetry-certified nurses will interpret the results of the ECG with instructions to contact Drs. [name] or [name] regarding abnormalities.

**Performance Task.** Psychomotor performance will be assessed at the same time as subjective drug-effects during all sessions with a computerized version of the Digit-Symbol-Substitution Test (DSST) (McLeod et al., 1982). In this procedure, the subject uses a numeric keypad to enter a geometric pattern displayed on a video screen. Subjects will have 90 seconds to enter as many geometric patterns as possible. The dependent measures are the number of geometric patterns the subject attempted to enter and the number of patterns entered correctly. This task will be completed immediately following the subjective questionnaires.

**Drug Dose and Administration.** All drugs will be administered under double-blind conditions and under medical supervision. COC doses will be given in random order. PHEN doses will be given in counterbalanced order across subjects. Doses of COC HCl will be prepared by weighing out the appropriate amount of powdered COC. The powder will then be mixed with lactose monohydrate powder, N.F. to make a total of 100 mg powder. Placebo will be prepared in an identical fashion, but will contain only lactose monohydrate powder. Doses of COC will be prepared individually for each subject. Doses of 0 [placebo], 20, 40 and 80 mg intranasal COC will be placed into individual glass vials labeled for each subject for each sampling session. Doses of PHEN (0, 35, 70 and 105 mg, administered two times daily) will be prepared by over-encapsulating commercially available tablets in a size 0 capsule. The capsule will then be loose filled with cornstarch. Placebo capsules will be prepared in an identical fashion, but will contain only cornstarch.

**Data Analysis.** Data will be analyzed as raw scores. Statistical significance refers to  $p \leq 0.05$ .

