## **17. DATA AND SAFETY MONITORING**

### *Data Monitoring Plan*

Data will be collected using a computerized data collection and management system wherever possible. This system automates the collection of data, which ensures the accuracy and completeness of data collection. The data are stored in a unique file on the hard drive of the computer and are printed after all the tasks are completed. In all instances, the data files do not contain the name of the subject, but instead, each subject is identified by a unique four-digit number. A computer file linking the unique number with the subject's name will be kept on a stand-alone, password-protected computer. All data requiring hand entry (e.g., cardiovascular measures) will be entered by two separate staff members and comparison macros will be run to ensure accuracy. Data files for experimental tasks and physiological measures from each experimental session will be manipulated and combined into a single electronic spreadsheet for each subject by one of the investigators. Data for all subjects will then be combined into a single electronic spreadsheet and separated by experimental measure for statistical analysis using SPSS (IBM, Armonk, NY).

In this protocol the primary outcome measure will be the influence of PHEN maintenance on the reinforcing effects of COC. The alpha level will be set at 5%.

As noted above, wherever possible, data are collected using an automated computer system, which increases the accuracy and completeness of data collection and ensures the validity and integrity of the data. The initial data manipulation described above will be conducted twice and compared. The quality of manipulated data and data analyses will be monitored by random inspection by the PI and/or Co-Investigators.

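### Does the stated 80% power for d = 0.44 with 36 subjects fail to reproduce, so that the sample-size justification must be restated?

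*Combined protocol and SAP*

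**What the plan says.** All of the relevant text is in the combined protocol and SAP.

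- **Section 7, Data Analysis, power statement.** The calculation is introduced with "Considering the complete within-subject design, number of dose levels of each drug", namely two PHEN conditions and four cocaine doses. It concludes that "enrolling 36 subjects will provide adequate power to detect an effect size" "of at least 0.44 for attenuation of the reinforcing effects of COC as a function of maintenance on PHEN and placebo", at power 0.80 and alpha 0.05, with G*Power as the source.
- **Same paragraph, basis for the size.** An earlier study from the same laboratory is cited: "That study demonstrated that d-amphetamine maintenance decreased the reinforcing effects of COC with an estimated effect size" of about 0.46.
- **Section 7, Data Analysis, decision rule.** Progressive-ratio outcomes go into a two-factor ANOVA with both factors within subject. Attenuation "will be inferred if the main effect of PHEN or the interaction of COC and PHEN attains statistical significance in the ANOVA".
- **Section 4.** The 36 are completers, so no dropout allowance enters the calculation.
- **Section 17, Data Monitoring Plan.** Only the 5% alpha level is repeated.

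The plan does not give the standardizer of d, the within-subject correlation, the number of measurements entered, any sphericity correction, the sidedness, or the G*Power test.

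**The concern.** The effect named in the power statement is a contrast between two maintenance conditions. In a fully within-subject ANOVA with 36 completers, that main effect has 1 and 35 degrees of freedom and is the same test as a two-sided paired t test. The obvious check is therefore a paired t calculation, and it does not return 80% at 0.44.

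The margin makes this look important. The plan supports 36 by placing its detectable effect (0.44) just below the earlier estimate (about 0.46), a gap of 0.02. On the paired reading the detectable effect is 0.48, the order reverses, and 36 would fall short of 80% for the very effect used to choose it. A reader who took that reading as the only one would conclude that the trial needs about 40 to 43 completers, or that its stated power is overstated by some seven points.

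**Working it through.** **Inputs.** From Section 7: n = 36, d = 0.44, earlier d ≈ 0.46, alpha = 0.05, target power 0.80, 2 × 4 within-subject cells. Correlations and sphericity factors are not in the documents. Every value below is an assumption, shown over a range.

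**1. Two-sided paired test, d on the SD of the differences.** Noncentral t with 35 df and noncentrality d√n.
- d = 0.44: 0.44 × 6 = 2.64, power 72.8%.
- d = 0.46: 0.46 × 6 = 2.76, power 76.5%.
- 80% is reached at d = 0.480. On this reading 80% needs 43 subjects for 0.44, or 40 for 0.46.

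The plan's figure is not reproduced. A one-sided version overshoots (82.7% at 0.44, detectable 0.423) and does not match an F test.

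**2. Two scores per subject, d on the raw-score SD, correlation r.** Convert by dz = d/√(2(1 − r)), then proceed as in step 1.

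| r (assumed) | dz at d = 0.44 | Power |
|---|---|---|
| 0 | 0.311 | 44% |
| 0.3 | 0.372 | 58% |
| 0.5 | 0.440 | 73% |
| 0.58 | 0.480 | 80% |
| 0.7 | 0.568 | 91% |

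The stated figure appears at r = 0.58.

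**3. Repeated-measures F test, f = d/2 = 0.22, m measurements, correlation ρ, sphericity factor ε.** λ = f²·n·m·ε/(1 − ρ), with df (m − 1)ε and 35(m − 1)ε.
- m = 4, ρ = 0.5, ε = 0.75: λ = 0.0484 × 36 × 4 × 0.75/0.5 = 10.45, df 2.25 and 78.75. Power is 80.2% and the detectable d is 0.439, which rounds to 0.44.
- ρ = 0.5, ε = 1: 73%, 88% and 98% for m = 2, 4 and 8.

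So a set of round-number inputs returns the plan's figure. They are not stated, and a four-level F is not the 1-df PHEN test. This shows that 0.44 can arise from ordinary inputs, not that these were the ones used.

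**4. PHEN main effect as the ANOVA would form it, d on a single-session SD.** Each maintenance condition is a mean over four sessions. With correlation w between sessions within a condition and c between sessions across conditions, the difference of the two means has variance 2[(1 + 3w)/4 − c] in units of the single-session variance, and dz = d/√variance.

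| w | c | Variance | dz at 0.44 | Power at 0.44 | Power at 0.46 |
|---|---|---|---|---|---|
| 0 | 0 | 0.50 | 0.622 | 95% | 97% |
| 0.3 | 0.3 | 0.35 | 0.744 | 99% | 99.5% |
| 0.5 | 0.3 | 0.65 | 0.546 | 89% | 91% |
| 0.7 | 0.4 | 0.75 | 0.508 | 84% | 87% |
| 0.7 | 0.3 | 0.95 | 0.451 | 75% | 79% |

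With equal correlations, power at 0.44 is at least 95% for any value from 0 upwards. It falls below 80% only in the last row, where sessions within a condition agree much more closely than sessions across conditions.

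**5. The interaction route.** The decision rule also accepts a significant interaction. If PHEN acts equally at every dose, and the two tests are taken as independent, the paired reading at 0.44 rises only to 0.728 + 0.272 × 0.05 = 74%. A true interaction would raise it further, by an amount the documents do not fix.

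**The case for a change.** The case for a change is that the power statement cannot be checked. Defensible readings of the same sentence run from 44% to over 95%, the comparison of 0.44 with 0.46 carries the whole justification for 36, and one or two sentences would settle it. The natural reading of a two-level contrast is the paired one, and it gives 73%.

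Part of this stands. The inputs are missing from a complete sentence with no redaction, and the paired figures are right.

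The consequence drawn from them does not stand:

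- The power statement says that it took account of the dose levels of both drugs, which a test on two scores per subject ignores.
- A condition that the PHEN–placebo correlation must reach about 0.54 for 36 to suffice at 0.46 holds only for one score per condition, or if the SD and correlation are those of the four-dose means. Step 4 shows more than 90% power at 0.46 with a cross-condition correlation of 0.3 or even 0.
- The reversal of 0.48 against 0.46 needs the earlier d to be on the paired-difference scale, which the documents do not say.
- The 74% figure for the either-test rule assumes an equal PHEN effect at every dose, including placebo cocaine. The plan predicts a rightward shift of the dose-response curve, which would ordinarily bring some interaction.
- Printing 0.48 in place of 0.44 would swap one unverified figure for another that rests on a single chosen reading.

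**Conclusion.** No change to the plan is called for. The narrow statement is correct: 80% at d = 0.44 cannot be reproduced from the inputs printed, and on the paired-difference reading the figures are 72.8% power and a detectable effect of 0.480. But that reading is an assumption. Others return the stated figure (four measurements, correlation 0.5, sphericity factor 0.75: 80.2%) or exceed it (single-session SD, four-dose means, equal non-negative correlations: 95% or more). Some fall below it, including two-score readings with correlation under 0.58 and the least favourable unequal-correlation case in step 4 (75%). The documents do not say which applies, so neither a miscalculation nor inadequate power is established.

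This is a gap in reporting a planning calculation. Filling it would leave the 36 completers, the ANOVA, the 5% level and the decision rule as they are. Once the data are in, precision is judged from the observed estimates and their standard errors, not from the G*Power input. The statistician who holds the original calculation can name its test, standardizer and correlation if asked.
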